
transfusion using non-study RBC (conventional) may be given to provide the patient with an appropriate and necessary treatment. In this case, a protocol deviation should be documented. If a study RBC transfusion is given after randomization before surgery commences, a protocol deviation should also be documented.
 
Treatment assessments will be divided into an acute transfusion support period starting the day of surgery (Day 0 up to Day 7) during which study RBC (Test or Control) are administered, a post-surgical follow-up period of a minimum of 28 days after the last study transfusion to collect additional safety data, a clinical assessment at day 30 after surgery specifically for mortality and RRT status, and a visit at day 75 (± 15) after the last study transfusion to assess mortality and RRT status, and collect samples for serological screening for antibodies specific to INTERCEPT RBCs.
 
In all patients, anesthesia and surgical procedures will be performed according to the local standards of care. Following the acute transfusion support period, subjects may receive conventional RBC components if additional transfusions are needed, as indicated by their treating physician.
 
Study Assessments: Monitoring and Follow-up
 
Baseline through Acute Transfusion Support Period (Pre-Op Day -1 up to Post-Op Day 7)
 
A screen for antibodies specific for INTERCEPT RBCs should be performed every time that a routine IAT is performed during the acute 7-day study transfusion period.
 
A blood sample for sCr will be taken at 48 ± 4 hours after completion of surgery for both transfused and non-transfused subjects. A sCr will be determined on a daily basis during the acute transfusion support period up to 7 days post-surgery. Other parameters including additional sCr will be collected on eCRFs only when available in the medical record.
 
Randomized subjects who do not receive an RBC transfusion following randomization within the first 48 hours after surgery will be discontinued from the study and replaced.
 
Daily sCr assessments will be recorded up to and including 48 ± 4 hours for transfused and non-transfused subjects. Other post baseline laboratory parameters and adverse events (AEs) will not be collected for non-transfused subjects. Vital status will be reported for randomized and non-transfused subjects at the time of discontinuation.
 
Hemodynamic and laboratory measures will be assessed pre-operatively (Day -1, Baseline) and daily as available in the medical record from post-operative Day 1 through Day 7, hospital discharge or death, whichever occurs first. If a subject is discharged prior to Day 7 but returns to the study site for a standard of care visit on Day 7, blood samples should be obtained on that day for a complete blood count and sCr determination.
 
Hemodynamic parameters that will be collected if available, include heart rate, blood pressure, mean arterial pressure, central venous pressure (CVP), and peripheral oxygen saturation via pulse oximetry probe.
				

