If multiple assessments (hemodynamic parameters, vital signs, laboratory parameters) are taken in a calendar day, the reported value for first collection of the day should be recorded in the eCRF with the exception of serum creatinine. Serum creatinine will be collected and recorded in the eCRF on a daily basis during the 7 day acute transfusion support period. If serum creatinine is measured multiple times in a day, the worst daily value should be recorded in the eCRF. In addition, a sample to measure sCr will be taken at 48 ± 4 hours after the end of surgery and captured on a specific CRF page for that time-point.

For non-transfused subjects, a blood sample for sCr will be drawn at 48 ± 4 hours hours post-surgery. Serum Creatinine up to and including 48 ± 4 hours post-surgery will be collected.

Urine output (mL/kg/hour) will be recorded in the eCRF daily while a urinary catheter is in place.

Other assessments during this trial period include details related to the specific surgical procedure (type of procedure, start and end times, RBC components transfused, all other blood components transfused, estimated blood loss from the surgical procedure, concomitant medications, intraoperative cell recovery and reinfusion, hemodilution, and nadir temperature). Additionally, daily estimated blood loss from chest tube(s) and from other sources, and day of chest tube removal will be recorded. See Table 7.1c for a detailed list of study assessments.

AEs and SAEs, including TRs and protocol-specified AEs (see Section 7.3), will be assessed from the start of surgery or the start of the first study RBC transfusion (whichever is first) on a daily basis and documented in the eCRF through post-operative Day 7. Adverse events (AEs) will not be collected for non-transfused

Cerus Corporation

Title: A Randomized, Double-Blinded, Controlled, Parallel Group, Non-inferiority, Phase III Study to Evaluate the Efficacy and Safety of the INTERCEPT Blood System for Red Blood Cells in Patients undergoing Complex Cardiac Surgery Procedures (the ReCePI study)

subjects, but vital status will be recorded at the time of discontinuation. See Table 7.1c for a detailed list of study assessments.

NOTE: The following post-operative assessments apply to randomized transfused subjects only.

6.1.3 Post-operative Period (Day 8 [or Post-discharge, if earlier] through Day 28 After Last Study Transfusion)

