The complete list of assessments to be performed during this post-operative period are outlined in Table 7.1d.

Laboratory results recorded in the eCRFs during this period will only be those assessed as clinically significant per the Investigator. Following the post-surgery 7-day acute transfusion support period, the post-operative period starts on Day 8 after surgery and goes through the Day 28±3 visit. Subjects will receive conventional non-study RBC components if additional transfusions are needed, as indicated by their treating physician.

Weekly telephone surveillance calls to the subject will be performed to collect AEs, SAEs and TRs. If a surveillance call falls on the same week as the Day 28±3 follow-up visit, the follow-up visit assessments will take precedent and a surveillance call is not required.

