^f If serum creatinine is measured multiple times in a day, the worst daily value should be recorded in the eCRF.

^g These assessments can be combined with screening assessments if screening visit is also on Day -1 or Day 0 Pre-Surgery.

^h Assessments that contribute to the AKI should be measured at approximately the same time every day during the treatment period.

ⁱ These assessments are required to be collected daily on Day 1 through Day 7 post surgery or until discharge. If subject returns after discharge for a postoperative standard of care visit, assessments will be collected in eCRFs on the appropriate study day.

^j Negative urine or serum pregnancy test.

Cerus Corporation

Title: A Randomized, Double-Blinded, Controlled, Parallel Group, Non-inferiority, Phase III Study to Evaluate the Efficacy and Safety of the INTERCEPT Blood System for Red Blood Cells in Patients undergoing Complex Cardiac Surgery Procedures (the ReCePI study)

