7.3.1.6 Definition of Acute Kidney Injury (AKI)

For the purposes of this study, a definition of an acute kidney injury during the study is based on the Kidney Disease: Improving Global Outcomes (KDIGO) AKI workgroup definition (KDIGO 2012) criteria as:

- An increase sCr $\geq 50\%$ of the pre-surgery baseline level within 7 days post-surgery, OR
- An increase in sCr ≥ 0.3 mg/dL (26.5 $\mu\text{mol/L}$) from pre-surgery baseline within 48 hours of surgery.

For the purposes of this study, acute kidney injury stages are defined as follows (KDIGO AKI workgroup):

Stage 1 Serum creatinine: 1.5–1.9 times baseline within 7 days after surgery
OR
 ≥ 0.3 mg/dl (≥ 26.5 $\mu\text{mol/L}$) increase within 48 hours of surgery

Stage 2 Serum creatinine: 2.0–2.9 times baseline within 7 days after surgery

Stage 3 Serum creatinine: 3.0 times baseline within 7 days after surgery
OR
Increase in serum creatinine to ≥ 4.0 mg/dl (≥ 353.6 $\mu\text{mol/L}$)
OR
Initiation of renal replacement therapy

If a renal event during the study fulfills KDIGO laboratory criteria as specified above, this may constitute an AE/SAE of AKI as per Investigator's clinical judgement.

Cerus Corporation

Title: A Randomized, Double-Blinded, Controlled, Parallel Group, Non-inferiority, Phase III Study to Evaluate the Efficacy and Safety of the INTERCEPT Blood System for Red Blood Cells in Patients undergoing Complex Cardiac Surgery Procedures (the ReCePI study)

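### The protocol gives conflicting rules for recording Day 3–7 creatinine in transfused patients, values that the 7-day AKI secondary endpoint needs

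*Protocol*

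**What the plan says.** **Synopsis, Study Assessments: Monitoring and Follow-up.** Three statements on creatinine stand close together:
- The first sets how often it is measured: "A sCr will be determined on a daily basis during the acute transfusion support period up to 7 days post-surgery"
- The second deals with values beyond the scheduled ones, which it makes conditional on the chart: a further creatinine goes onto the eCRF if the medical record happens to hold it.
- The third sets what is recorded: "Daily sCr assessments will be recorded up to and including 48 ± 4 hours for transfused and non-transfused subjects"

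**Section 6.1.2** (acute transfusion support period): "Serum creatinine will be collected and recorded in the eCRF on a daily basis during the 7 day acute transfusion support period". It adds that, where a day has several measurements, the worst one is entered. For a patient discharged early who comes back before Day 7, the same section asks for routine laboratory values to be entered.

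**Table 7.2** marks creatinine as required on Days 1–7. Footnote f repeats the worst-value rule. Footnote i makes collection daily to Day 7 or discharge and says that, for a return visit after discharge, "assessments will be collected in eCRFs on the appropriate study day". Footnote e says the same of routine values.

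**Section 6.1.3**, whose heading starts the period at Day 8 or at discharge if that is earlier: "Laboratory results recorded in the eCRFs during this period will only be those assessed as clinically significant per the Investigator". Table 7.1d carries the same start in its title and the same filter in footnote 10, which is attached to the haematology and chemistry rows.

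**Sections 4.1.2 and 7.3.1.6** make KDIGO stage I–III AKI a secondary efficacy endpoint. One entry criterion is a creatinine rise of at least 50% "of the pre-surgery baseline level within 7 days post-surgery"; the stage 1, 2 and 3 ratio criteria use the same 7-day window.

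**The concern.** The AKI endpoint can only be derived from creatinine values that reach the database. Two pieces of text, if followed, would keep some Day 3–7 values out of it.

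The Synopsis sentence puts transfused patients under the 48 ± 4 hour limit. A patient who has not qualified by then but reaches 1.5 times baseline on Days 3–7 could go uncounted. A patient already at stage 1 who later reaches 2 or 3 times baseline could be under-staged.

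The section 6.1.3 filter does something different. Once a patient has been discharged, whether a creatinine is recorded depends on whether the investigator thinks it matters. Recording then depends on the value itself, which is undesirable for an endpoint built from those values. Sites could also differ according to which passage they work from.

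**Working it through.** No figure stated in the plan depends on this point. The sample size of 146 per arm rests on the 48-hour primary endpoint. The check is therefore a comparison of passages.

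**Step 1: does the endpoint need Day 3–7 values?** Yes. Section 7.4 places the 48 ± 4 hour sample on post-operative Day 2, while the ratio criteria in 7.3.1.6 run to Day 7. Days 3–7 are 5 of the 7 post-operative daily values (5/7 = 71%). That counts days and not cases.

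**Step 2: the 48 ± 4 hour limit.**

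| Place | Whom it covers | Daily creatinine |
|---|---|---|
| Synopsis, first statement above | not restricted | measured to Day 7 |
| Synopsis, third statement above | transfused and non-transfused | recorded to 48 ± 4 h |
| 4.5, 5.3.2, 6.1.1, 6.1.2, 7.1 | text on non-transfused subjects | recorded to 48 ± 4 h |
| 6.1.2, later paragraph | patients in the 7-day support period | recorded daily, worst value |
| Table 7.2, footnotes f and i | Days 1–7 | required daily to Day 7 or discharge |

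Only the Synopsis attaches the limit to transfused subjects. It reads like the non-transfused rule with one group added.

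**Step 3: discharge before Day 7.** Take a creatinine drawn at a return visit on, say, Day 5.
- Section 6.1.2 and Table 7.2 footnotes e and i: record it.
- Section 6.1.3 heading and text, and Table 7.1d title and footnote 10: record it only if judged clinically significant.
- The body text of 6.1.3 says the period begins on Day 8, so 6.1.3 disagrees with its own heading.
- The significance note in Table 7.2 sits in a column for Days 8 to 28 and does not reach Day 5.

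**Step 4: what is unaffected.** The primary endpoint is read within 48 ± 4 h. The AKI criterion of at least 0.3 mg/dL within 48 h is still captured. Need for RRT is documented separately at Day 30 (6.1.5).

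**Step 5: size.** The documents do not say what share of 7-day AKI first qualifies after 48 h. As an illustration only, assume a true AKI rate of 30–40% and a late share of 5–30%, and suppose that every site applied the Synopsis sentence as a strict limit and entered no later value:
- missed cases = 292 × AKI rate × late share
- low end: 292 × 0.30 × 0.05 = 4.4
- high end: 292 × 0.40 × 0.30 = 35.0
- at a true rate of 30%, the recorded rate would be 0.30 × 0.95 = 28.5% down to 0.30 × 0.70 = 21%

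If sites follow section 6.1.2, the loss for inpatients is zero.

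**The case against.** The strongest answer is that the operative text is clear. Section 6.1.2 and Table 7.2 state the daily Day 1–7 rule for creatinine explicitly, and a site working from them enters every inpatient value. The Synopsis sentence can even be read as the recording common to both groups, since it stands between sentences about non-transfused subjects. For early discharges, the more specific rule (6.1.2, footnotes e and i) might be taken to override the heading of 6.1.3.

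Much of this stands, and it rules out several stronger readings that a reader might infer:
- *That the plan ends creatinine recording at 48 hours in transfused patients.* The body requires the opposite, and the Synopsis contradicts itself.
- *That a site following the Synopsis would record nothing later.* The Synopsis still collects additional creatinine values when they are in the medical record.
- *That inpatient Day 3–7 values are filtered.* They are not; the filter conflict concerns patients discharged before Day 7.
- *That missing late values will be analysed as no AKI, or that the AKI comparison is biased by a known amount.* The protocol does not say how missing secondary data are handled, the SAP is not at hand, and no non-inferiority margin is stated for AKI.

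What does not stand is that nothing needs changing. The Synopsis sentence names transfused subjects in plain terms, and the protocol has no rule that the body prevails over it. The two post-discharge rules both apply to the same sample.

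**Conclusion.** The protocol contradicts itself on data capture in two places that bear on one secondary efficacy endpoint. The Synopsis sentence conflicts with the Synopsis's own Day 7 rule, section 6.1.2 and Table 7.2. Section 6.1.3 and Table 7.1d conflict with section 6.1.2 and Table 7.2 footnotes e and i for patients discharged before Day 7. Either could leave late AKI missed or under-staged, and in the second case whether a value is recorded depends on the value.

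The weight is moderate to low. The design itself, daily creatinine to Day 7 or discharge, is sound. The size cannot be derived from the documents: the 4 to 35 cases of 292 rest wholly on assumed AKI rates, an assumed late share and uniform adherence to the Synopsis sentence, and the inpatient loss is zero under the body text. The correction should still be made, because the endpoint depends on these values and the wording is easily put right.

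**What to change.** 1. In the Synopsis, replace the sentence so that daily creatinine is recorded through post-operative Day 7 or discharge for transfused subjects, and through the 48 ± 4 hour sample for non-transfused subjects.
2. In section 6.1.3 and Table 7.1d footnote 10, exempt creatinine obtained up to post-operative Day 7 from the clinical-significance filter, in line with section 6.1.2 and Table 7.2 footnotes e and i.

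The Table 7.2 column for Days 8 to 28 needs no change. Removing the mention of additional creatinine from the Synopsis sentence on when-available parameters is optional.

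The cost is a few wording edits at the next amendment. No samples are added, because Table 7.2 already requires the in-hospital ones and the return-visit values are routine care. Section 4.7 makes the medical record the source, so values measured but not entered should be recoverable by data query.

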1 LIST OF ABBREVIATIONS AND DEFINITIONS OF TERMS

AABB	American Association of Blood Banks
ADL	Activities of Daily Living
AE	Adverse Event
AHG	Anti-human Globulin
AHTR	Acute Hemolytic Transfusion Reaction
AKI	Acute Kidney Injury
AKIN	Acute Kidney Injury Network
ALP	Alkaline Phosphatase
ALT	Alanine Transaminase
ANOVA	Analysis of Variance
ANCOVA	Analysis of Covariance
AS	Additive Solution
AST	Aspartate Aminotransferase
ATP	Adenosine Triphosphate
ATR	Acute Transfusion Reaction
BP	Blood Pressure
bpm	Beats per minute
BUN	Blood Urea Nitrogen
BVDV	Bovine Viral Diarrhea Virus
C	Celsius
CABG	Coronary Artery Bypass Graft
CBC	Complete Blood Count
CDC	Centers for Disease Control and Prevention
CFR	Code of Federal Regulations
CFU	Colony Forming Units
CI	Confidence Interval
CLIA	Clinical Laboratory Improvement Amendments
CMH	Cochran-Mantel-Haenszel
CMV	Cytomegalovirus
CPB	Cardiopulmonary Bypass
CP2D	Citrate Phosphate Double Dextrose
CPD	Citrate Phosphate Dextrose
CRF	Case Report Form
CRO	Contract Research Organization
CSF	Cerebrospinal Fluid
CTCAE	Common Terminology Criteria for Adverse Events
CVP	Central Venous Pressure
DAT	Direct Antiglobulin Test. Also referred to as the direct Coombs test.

Cerus Corporation

Title: A Randomized, Double-Blinded, Controlled, Parallel Group, Non-inferiority, Phase III Study to Evaluate the Efficacy and Safety of the INTERCEPT Blood System for Red Blood Cells in Patients undergoing Complex Cardiac Surgery Procedures (the ReCePI study)

Device Malfunction	The failure of a medical device to function according to its requirements.
DHBV	Duck Hepatitis B Virus
DHTR	Delayed Hemolytic Transfusion Reaction
dL	Deciliter
DNA	Deoxyribonucleic Acid
ds DNA	Double stranded DNA
2,3-DPG	2,3-Diphosphoglycerate
DSMB	Data and Safety Monitoring Board
DSTR	Delayed Serological Transfusion Reaction
EC	Ethics Committee
ECMO	Extracorporeal Membrane Oxygenation
eCRF	Electronic Case Report Form
EDC	Electronic Data Capture
EIA	Emerging Infectious Agents
EKG	Electrocardiogram
EOS	End of Study
F	Fahrenheit
FDA	Food and Drug Administration
FNHTR	Febrile Non-Hemolytic Transfusion Reaction
g	Gram
GCP	Good Clinical Practice
GSH	Glutathione
HA	Hemolytic anemia
Hb	Hemoglobin
HBV	Hepatitis B Virus
Hct	Hematocrit
HCV	Hepatitis C Virus
HELLP	A syndrome occurring in pregnancy. A combination of the breakdown of red blood cells (hemolysis: the H in the acronym, elevated liver enzymes (EL), and low platelet count (LP).
HIV	Human Immunodeficiency Virus
HLA	Human Leukocyte Antigen
HR	Heart rate
HSV	Herpes Simplex Virus
HTR	Hemolytic Transfusion Reaction
IABP	Intra-aortic Balloon Pump
IAT	Indirect Antiglobulin Test. Also referred to as the Indirect Coombs Test.
IBS	INTERCEPT Blood System (abbreviation used in preceding protocol versions)
ICF	Informed Consent Form

Cerus Corporation

Title: A Randomized, Double-Blinded, Controlled, Parallel Group, Non-inferiority, Phase III Study to Evaluate the Efficacy and Safety of the INTERCEPT Blood System for Red Blood Cells in Patients undergoing Complex Cardiac Surgery Procedures (the ReCePI study)

ICH	International Council on Harmonization
ICU	Intensive Care Unit
IEC	Independent Ethics Committee
IgA	Immunoglobulin A
IgG	Immunoglobulin G
IgM	Immunoglobulin M
INTERCEPT Blood System for RBCs	Name of the current Cerus' Investigational device
INTERCEPT RBC(s)	Red blood cell component (s) that have been processed/treated with the INTERCEPT Blood System for Red Blood Cells (also known as INTERCEPT RBCs or S-303 (treated) RBCs)
IP	Investigational product
IRB	Institutional Review Board
IWRS	Interactive Web Response System
KDIGO	Kidney Disease Improving Global Outcomes
kg	Kilogram
LDH	Lactate Dehydrogenase
L	Liter
LVAD	Left Ventricular Assist Device
mg	milligram
miITT	Modified Intent-to-Treat
mL	Milliliter
mM	Millimole
µM	Micromole
MI	Myocardial Infarction
mm ³	Cubic millimeter
mm Hg	Millimeter of mercury
N	Number
NBG	Normalized Background
NCI	National Cancer Institute
PaCO ₂	Partial pressure of carbon dioxide
PFU	Plaque Forming Unit
PP	Per Protocol
RBC	Red Blood Cell
ReCePI	Red Cell Pathogen Inactivation (acronym)
RIFLE	Risk, Injury, Failure, Loss of kidney function, and End-stage kidney disease classification
RNA	Ribonucleic Acid
ROS	Reactive oxygen species
RR	Respiratory rate

Cerus Corporation

Title: A Randomized, Double-Blinded, Controlled, Parallel Group, Non-inferiority, Phase III Study to Evaluate the Efficacy and Safety of the INTERCEPT Blood System for Red Blood Cells in Patients undergoing Complex Cardiac Surgery Procedures (the ReCePI study)

RRT	Renal Replacement Therapy
ssRNA	Single Stranded Ribonucleic Acid
S-300	(N-(9-Acridinyl)- β -alanine). The primary decomposition product of S-303.
S-303	Amustaline. [N,N-bis (2-chloroethyl)]-2-aminoethyl 3-[(acridin-9-yl) amino] propionate free base. May also refer to S-303 in solution (dissolved S-303 2HCl).
S-303•2HCl	S-303 in the salt form used for treating RBC components.
SAG- M	SAG-Mannitol: an RBC additive solution
SAE	Serious Adverse Event
SD	Standard deviation
SCD	Sickle Cell Disease
sCr	Serum creatinine
SIRS	Systemic Inflammatory Response Syndrome
SOC	System Organ Class (MedDRA)
SOP	Standard Operating Procedure
TACO	Transfusion Associated Circulatory Overload
TA-GVHD	Transfusion Associated Graft versus Host Disease
TEAE	Treatment Emergent Adverse Event
TR	Transfusion Reaction
TRALI	Transfusion Related Acute Lung Injury
TRS	Transfusion Related Sepsis
TRUST	Transfusion Risk Understanding Screening Tool
TTI	Transfusion-Transmitted Infection
UADE	Unanticipated Adverse Device Effect
ULN	Upper Limit of Normal
UO	Urinary output
U.S.	United States
USP	US Pharmacopeia
VSV	Vesicular Stomatitis Virus
WBC	White Blood Cells
WNV	West Nile Virus

Cerus Corporation

Title: A Randomized, Double-Blinded, Controlled, Parallel Group, Non-inferiority, Phase III Study to Evaluate the Efficacy and Safety of the INTERCEPT Blood System for Red Blood Cells in Patients undergoing Complex Cardiac Surgery Procedures (the ReCePI study)

2 BACKGROUND INFORMATION

2.1 GENERAL

Red blood cell (RBC) transfusion is a critical supportive therapy for healthcare. Patients and physicians assume, when required, blood transfusion will be available and safe. However, serious transfusion-transmitted infections (TTI) caused by viruses, bacteria and protozoa (Stramer 2009, MacLennan 2006); and fatal transfusion complications such as transfusion-associated graft-versus-host disease (TA-GVHD) still pose a threat to transfusion recipients (Kopolovic 2015). Currently, prevention of TTI includes pre-donation evaluation and selection of low-risk donors, followed by serologic and/or nucleic acid testing for selected known infectious pathogens.

The advent of testing has greatly reduced TTI from blood products, particularly viral disease, and sepsis associated with the transfusion of bacterially contaminated red cell blood components is generally regarded as a very rare event. However, from 1976 through September 1998, 26 fatalities thought to be secondary to contaminated whole blood or red cells were reported to the U.S. FDA (Lee 1999). The majority of deaths reported to the FDA involved *Yersinia enterocolitica*. The highest reported incidence of *Y. enterocolitica* contamination was reported in New Zealand, with an incidence rate of 1 in 65,000 and a fatality rate of 1 in 104,000 red cell units transfused (Theakston et al. 1997). Unrecognized cases, underreporting, and regional variation may account for observed differences in this incidence.

Interestingly, passive reporting studies of bacterially contaminated red cells from the United States, France, and the United Kingdom that caused symptoms of infection show a relative paucity of *Y. enterocolitica* cases (Perez et al. 2001, Kuehnert et al. 2001, Serious Hazards of Transfusion report for 2000-2001). Of the reported deaths, one was due to a coagulase-negative *Staphylococcus* strain and seven were due to a variety of gram-negative organisms (including *Serratia liquefaciens* in three cases). These organisms are all capable of growth at refrigerated temperatures (1° to 6°C). Sepsis associated with the transfusion of red cells contaminated with gram-negative bacteria is typically severe and rapid in onset (Brecher and Hay 2005). Patients frequently develop high fever (temperatures as high as 109°F have been observed) and chills during or immediately following transfusion. From 1987 to February 1996, 20 recipients of *Y. enterocolitica* red cells were reported to the Centers for Disease Control (Cookson et al, 1996). Twelve of the 20 recipients died, and the median time to death was only 25 hours. Of the seven who developed disseminated intravascular coagulopathy, six died.

Cerus Corporation

Title: A Randomized, Double-Blinded, Controlled, Parallel Group, Non-inferiority, Phase III Study to Evaluate the Efficacy and Safety of the INTERCEPT Blood System for Red Blood Cells in Patients undergoing Complex Cardiac Surgery Procedures (the ReCePI study)

Prospective bacterial cultures of whole blood or red cells, however, have shown a much higher incidence of bacterial contamination (Damgaard et al 2015). The organisms commonly cultured are *Staphylococcus* sp. or *Propionibacterium* sp.; those strains that have been reported to be isolated in association with adverse events linked to the transfusion of contaminated red cell concentrates include *Pseudomonas* sp., *S. marcescens*, *Enterobacter* sp., *Klebsiella* sp., *S. epidermidis* and *B. cereus* (Siblini et al 2004).

Newly-emerging infectious agents also remain important risks to blood safety. Estimates of per-unit and per-patient aggregate infectious risks for conventional RBCs, including known and potential emerging infectious agents (EIA, modeled based on chikungunya and dengue viruses) were calculated by Kleinman and Stassinopoulos (2015). Minimum and maximum per-unit risks were calculated as 0.0003% (1/323,000) and 0.12% (1/831), respectively. The minimum estimate is for known lower-risk pathogens while the maximal estimate also includes an EIA and endemic area *Babesia* sp. risk. For patients with hemoglobinopathies who receive repeated RBC transfusions such as sickle cell disease (SCD), at the minimum risk level it is estimated that approximately 1/450 (0.22%) of patients will acquire an infection during their entire course of transfusion therapy (approximately 30-50 years); at the maximum risk levels, infections risk increases to 43-45% for patients with hemoglobinopathies, or almost 1 in every 2 patients (Kleinman and Stassinopoulos 2015).

Leukoreduced RBC concentrates contain $<5 \times 10^6$ white blood cells (WBC) that may induce TA-GVHD and/or alloimmunization to human leukocyte antigen (HLA) antigens. Gamma irradiation can effectively prevent TA-GVHD in transfusion recipients. However, almost half the cases of TA-GVHD occur in patients in which their treating physicians failed to identify risk using current guidelines for blood irradiation, leading to substantial morbidity and mortality (Kopolovic 2015). Moreover, irradiation adversely affects post-transfusion RBC recovery (Dumont 2008) and is associated with raised extracellular potassium levels in the transfused concentrates.

To proactively address the risk of TTIs and TA-GVHD, Cerus has developed pathogen and leukocyte inactivation technology systems (INTERCEPT Blood System™) for platelet and plasma components and is currently developing a system for RBC concentrates. These systems use nucleic acid-targeted compounds that intercalate into, and upon activation, covalently bind to nucleic acids of viruses, bacteria, parasites and leukocytes that may contaminate blood components, and form irreversible adducts and crosslinks thus preventing replication and TTI. This

Cerus Corporation

Title: A Randomized, Double-Blinded, Controlled, Parallel Group, Non-inferiority, Phase III Study to Evaluate the Efficacy and Safety of the INTERCEPT Blood System for Red Blood Cells in Patients undergoing Complex Cardiac Surgery Procedures (the ReCePI study)

process does not depend on or generate reactive oxygen species (ROS) which can damage cells and proteins. RBCs do not require nucleic acid for therapeutic function and thus retain therapeutic efficacy after pathogen inactivation treatment.

INTERCEPT treated RBC (INTERCEPT RBCs) components should not require gamma irradiation because the treatment process inactivates donor white blood cells with a high safety margin (Castro et al. 2016). It is also possible that INTERCEPT treatment may interfere with antigen presentation by donor leukocytes, thereby reducing the incidence of HLA alloimmunization.

Conventional leukoreduced RBC concentrates include approximately 20-40 mL of residual plasma that contains serum proteins and immunoglobulins; these are implicated in allergic TRs and Transfusion Related Acute Lung Injury (TRALI). The INTERCEPT RBC process includes a terminal washing step that reduces the concentration of plasma proteins and may reduce the incidence of these reactions.

The INTERCEPT Blood System for RBCs inactivates a variety of bacteria, viruses and protozoa. The organisms evaluated to date include examples representing a range of different characteristics, such as enveloped (HIV and DHBV) and non-enveloped (Bluetongue virus), RNA genome (HIV and BVDV) and DNA genome (DHBV), and single stranded (HIV) and double stranded (DHBV) genomes. The bacteria evaluated represent Gram negative bacilli (*Yersinia* sp., *Serratia* sp., *E. coli*, *Salmonella* sp. and *Pseudomonas* sp.) and Gram positive cocci (*S. epidermidis* and *S. aureus*) that are significant especially for RBC transfusion. The protozoan parasites evaluated to date are *Plasmodium falciparum* and *Babesia microti*. INTERCEPT RBCs have demonstrated adequate viability in terms of in vivo recovery and lifespan for transfusion (Cancelas 2015), and a recently completed Phase 3 clinical study (CLI 00076) in cardiovascular surgery patients conducted in Europe has demonstrated that INTERCEPT RBCs possess in vitro characteristics comparable to untreated RBCs with a comparable safety profile (Brixner 2015, Rico 2015).

The proposed phase 3 study in patients undergoing complex cardiac surgery is intended to demonstrate that INTERCEPT RBCs are non-inferior to conventional RBCs with regard to clinical safety and clinical efficacy for transfusion support of acute anemia during surgery with potential hemodynamic instability. The study is designed to support the licensure of the INTERCEPT Blood System for Red Blood Cells.

Cerus Corporation

Title: A Randomized, Double-Blinded, Controlled, Parallel Group, Non-inferiority, Phase III Study to Evaluate the Efficacy and Safety of the INTERCEPT Blood System for Red Blood Cells in Patients undergoing Complex Cardiac Surgery Procedures (the ReCePI study)

